### **TREATMENT ALLOCATION**

Treatment received will depend on the findings on the venous Duplex scan. All treatments are minimally invasive with endovenous ablation procedures (either radio-frequency ablation, endovenous laser ablation or mechano-chemical ablation), avulsions or ultrasound-guided foam sclerotherapy. All procedures will be carried out under local anaesthetic and patients will be discharged home later that day, as is the current standard of care.

## **MEASUREMENT OF OUTCOMES**

### **Primary Outcome**

- Measure the quality-adjusted life years (QALY) gained at 3 months (by patients randomised to treatment in the One Stop Vein Clinic with patients randomised to treatment in the Normal Care Pathway)

### **Secondary Outcome**

- Patient satisfaction with the service provided using the Picker patient experience questionnaire both post-operatively and at the 3 months follow-up (One Stop Vein Clinic versus Normal Care Pathway)
- Measure and compare the quality of life scores using EQ-5D, AVVQ and CIVIQ at 0 and 3 months in patients randomised to treatment in the One Stop Vein Clinic with patients randomised to the Normal Care Pathway
- Time from referral to treatment
- Assess the cost-effectiveness of the One Stop Vein clinic compared to the normal care pathway
- Record the time to return to normal activities and to work
- Assess the estimated societal costs

## **STUDY DURATION & SAMPLE SIZE**

Following screening of their GP referral letter, patients with varicose vein disease will be invited to participate in the study. We estimate that 12-14 patients will be invited on a weekly basis to participate in the study following screening. Out of those, we are anticipating only 8 patients will agree to be randomised to the One Stop Vein Clinic or Normal Care Pathway. If the clinic is held weekly, we estimate recruiting 416 patients over the course of the year (8 patients X 52 weeks).

Statistical analysis suggests that the sample size of 208 patients per group would be able to power a potential phase 3 multicentre randomised controlled trial. Compared to a previous study conducted in our unit which involved 317 patients in total and looked at different quality of life scores and their responsiveness, the coefficient of variation (ratio of standard deviation to mean) was found to increase at the follow-up period and to vary among the different scores used. With a larger sample size as in this pilot study, this variability would be reduced and result in a smaller coefficient of variation when looking at the follow-up scores. Hopefully, this will enable us to identify the QoL score with the least variability and use it as the primary outcome measure in a future Phase 3 study. A primary outcome measure with little variability would provide us with enough information to estimate an adequate sample size for any future randomised controlled trials.

For example, with a sample size of 208 patients and coefficient of variation of 0.5, a 15% reduction in the geometric mean (a measure of central tendency, similar to median) would be required compared to 25% from the Shepherd et al. study. With power at 85%, this would allow us to determine an adequate sample size.

Participants will be followed-up post-procedure for 3 months, including for patients randomised to the Normal Care Pathway (with potentially longer waiting time from referral to treatment). This means that the study period will be about 18 months. With 3 months for study start-up and 3 months to write the study up, the study will last for 24 months.

Approximately 1,000 patients undergo varicose vein procedures at the Imperial College NHS Trust every year.

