## **METHODS**

GP referrals will be screened and patients meeting the inclusion criteria will be invited to take part in the trial.

They will be sent an information pack containing:

- Information leaflet about the trial
- Information about varicose veins, their treatments and a telephone number as a helpline
- The Aberdeen Varicose Vein Questionnaire (AVVQ), the Chronic Venous Disease Quality of Life Questionnaire (CIVIQ) and EuroQoL's quality of life questionnaire (EQ-5D)
- Consent form to participate in the study

Patients agreeing to be part of the trial will be consented and randomised either to:

- The One Stop Vein Clinic (offering same day diagnosis and treatment);  
or
- The normal care pathway

Once patients indicate their consent to participate, their General Practitioners (GP) will be sent a letter informing them of the patient's participation in this study.

Patients declining to partake in the randomised part of the study, but agreeable to complete study questionnaires while continuing down the normal care pathway, will also be consented. Further information will be provided to them when they attend for their clinic appointment and the consenting process will take place when they attend for their subsequent procedure

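### The only variability measure named for choosing and sizing the phase 3 outcome is the raw follow-up coefficient of variation; the baseline-to-3-month correlation and residual SD should be carried forward too

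*Protocol*

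**What the plan says.** STUDY DURATION & SAMPLE SIZE describes what the pilot will hand on to a later trial. It defines variability as the ratio of standard deviation to mean, notes that in a previous study from the same unit this ratio rose at follow-up and differed between scores, and expects the pilot to give a "smaller coefficient of variation when looking at the follow-up scores". The score that varies least is then to become the phase 3 primary outcome, and "A primary outcome measure with little variability would provide us with enough information to estimate an adequate sample size" for later trials.

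The section's worked example starts "with a sample size of 208 patients and coefficient of variation of 0.5" and refers to "a 15% reduction in the geometric mean" at 85% power. It contains no baseline score and no correlation. The section also says that a "sample size of 208 patients per group would be able to power a potential phase 3 multicentre randomised controlled trial".

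Elsewhere the same scores are planned at baseline. METHODS puts "The Aberdeen Varicose Vein Questionnaire (AVVQ), the Chronic Venous Disease Quality of Life Questionnaire (CIVIQ") and the EQ-5D into the information pack that goes out with the consent form. The Secondary Outcome list says "Measure and compare the quality of life scores using EQ-5D, AVVQ and CIVIQ at 0 and 3 months". The flow chart before Appendix 1 instead lists the three questionnaires under the day of treatment, which comes after randomisation.

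**The concern.** The protocol gives the follow-up coefficient of variation two jobs: choosing the phase 3 primary outcome and informing its sample size. When the same score is also measured before randomisation, an analysis that adjusts for it works with the residual variance, meaning the part of the 3-month score that the patient's own baseline does not explain. The raw follow-up spread leaves this out.

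Two things are at stake. The first is efficiency: a phase 3 sized on raw variance is larger than an adjusted analysis would need. The second is the choice of outcome, and it matters more. Scores can differ in how well baseline predicts follow-up, so the score with the smallest raw coefficient of variation need not be the one that needs fewest patients. Calling the raw figure conservative answers the first point but not the second.

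**Working it through.** **Inputs from the protocol (STUDY DURATION & SAMPLE SIZE):** 208 per group; coefficient of variation (CV) 0.5; 15% change in the geometric mean; 85% power.

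**Assumptions, because the protocol gives no figure:** two-sided alpha 0.05; no dropout; r between 0.3 and 0.7, taken on the log scale.

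**1. Reproduce the worked example without a baseline term.**
- Variance of the log score = ln(1 + 0.5²) = 0.223, so SD = 0.472.
- z sum = 1.960 + 1.036 = 2.996.
- n per group = 2 × 2.996² × 0.223 / (ln ratio)².
- Ratio 1.15: ln 1.15 = 0.1398, giving n = 206 (207 with the t distribution). Power at 208 is 85.5%.
- Ratio 0.85, a literal 15% reduction: ln 0.85 = -0.1625, giving n = 152. Power at 208 is 93.9%.

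The stated 208 is recovered as an unadjusted two-group comparison if 15% is read as a ratio of 1.15. Either way the example has no baseline term.

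**2. Add the baseline score.** With adjustment for baseline, n is multiplied by (1 - r²) and the detectable log difference by sqrt(1 - r²).

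| r | 1 - r² | fall in n | n per group, ratio 1.15 | n per group, ratio 0.85 | detectable increase at 208 | detectable reduction at 208 |
|---|---|---|---|---|---|---|
| 0 | 1.00 | none | 206 | 152 | 14.9% | 13.0% |
| 0.3 | 0.91 | 9% | 187 | 139 | 14.2% | 12.4% |
| 0.5 | 0.75 | 25% | 154 | 114 | 12.8% | 11.3% |
| 0.7 | 0.51 | 49% | 105 | 78 | 10.4% | 9.4% |

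At r = 0.2 the fall is only 4% (206 to 197).

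**3. Effect on the choice of score (illustrative values, not from the protocol).**
- Score A: CV 0.50, r = 0.7. Raw log variance 0.223; adjusted 0.223 × 0.51 = 0.114.
- Score B: CV 0.45, r = 0.2. Raw log variance ln(1 + 0.45²) = 0.184; adjusted 0.184 × 0.96 = 0.177.

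The protocol's criterion picks B because its raw CV is lower. For the same relative effect, B needs 0.177 / 0.114 = 1.56 times as many patients as A, about 56% more.

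**4. Can the pilot supply r?** Yes, if both time points are complete. With 416 pairs and r = 0.5, the 95% confidence interval is about 0.42 to 0.57.

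**The case against.** The strongest reply is that nothing has been decided. The section voices a hope and gives an illustration; it sets no phase 3 size, formula or analysis model. Both time points are planned, so r and the residual SD can be estimated under the present wording. This stands: the plan names an incomplete quantity, but it loses no data.

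A second reply is that unadjusted variance is conservative and valid, and that covariate adjustment commonly belongs in the SAP, which is not shown. This holds for the pilot's own analysis. It does not cover the criterion for selecting and sizing the phase 3 outcome, because the protocol states that itself.

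A third reply is that the gain may be small. Under the normal care pathway, treatment may come up to 18 weeks after referral and follow-up 3 months after that, so the interval from the information pack differs by arm and r may be low. This also stands, and it is a reason to estimate r.

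A reader might go further and infer that the Secondary Outcome list prescribes a between-arm test at time 0, or an unadjusted test at 3 months. It does neither. Comparing scores at 0 and 3 months fits change scores or baseline adjustment equally well, and the primary QALY outcome is silent on adjustment. No change to the outcome sections follows.

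**Conclusion.** The point holds in a limited form. The raw follow-up CV is the only variability measure the protocol names for choosing and sizing the phase 3 outcome, and its worked example reproduces with no baseline term. For any r above zero the baseline-adjusted variance is smaller, and the ranking of scores can change.

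The size depends on r, which the protocol does not give. Over an assumed 0.3 to 0.7, required n falls by 9% to 49% (206 to between 187 and 105 per group). These figures also assume two-sided 5%, no dropout and the 1.15 reading of the example.

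Three stronger readings might be inferred and are not supported:
- That phase 3 is already fixed at too large a size. The text leaves its size to be estimated, and without r no excess can be put on it.
- That every patient has a clean pre-randomisation score. METHODS sends the questionnaires before consent, but the flow chart places them on the day of treatment. A score taken after randomisation, at delays that differ by arm, is not a sound baseline covariate.
- That the pilot's own size is affected. The 416 comes from expected accrual: "we estimate recruiting 416 patients over the course of the year (8 patients X 52 weeks").

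**What to change.** In STUDY DURATION & SAMPLE SIZE, state that for each score the pilot will estimate (a) the correlation between the pre-randomisation and 3-month scores and (b) the residual SD of the 3-month score after regression on the pre-randomisation score and arm. State that these will be used to choose and size the phase 3 primary outcome, with the raw CV reported alongside.

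Reconcile METHODS with the flow chart on when AVVQ, CIVIQ and EQ-5D are completed at baseline, and define month 0, so that the covariate is the score obtained before randomisation.

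The cost is a few sentences of protocol text and one regression per score. No new questionnaires, visits or patients are needed.

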## **DESCRIPTION**

A pilot randomised controlled trial looking at the setting up of a one stop vein clinic for the treatment of varicose veins and assessing the quality-adjusted life years at 3 months of patients

This will be a pilot study which is designed to provide us with enough information for a potentially larger multicentre randomised controlled study.

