## **OBJECTIVES**

- Primary Objective
  - Measure the quality-adjusted life years (QALY) gained at 3

months (using EuroQoL's EQ-5D) & AVVQ by patients randomised to treatment in the One Stop Vein Clinic with patients randomised to treatment in the normal care pathway

- Secondary Objective
  - Patient satisfaction with the service provided using the Picker patient experience questionnaire both post-operatively and at the 3 months follow-up (One Stop Vein Clinic versus Normal Care Pathway)
  - Measure and compare the quality of life scores using CIVIQ at 0 and 3 months in patients randomised to treatment in the One Stop Vein Clinic with patients randomised to the Normal Care Pathway
  - Record the time from referral to treatment (RTT)
  - Assess the cost-effectiveness of the One Stop Vein clinic compared to the normal care pathway
  - Record the time to return to normal activities and to work
  - Assess the estimated societal costs

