## Appendix 8. CIVIQ-14 Questionnaire

### C I V I Q-14 SELF-QUESTIONNAIRE PATIENTS *In English language for UK*

Many people complain of leg pain. We would like to find out how often these leg problems occur and to what extent they affect the everyday lives of those who suffer from them.

Below you will find a list of symptoms, sensations or types of discomfort that you may be experiencing and which may make everyday life hard to bear to a greater or lesser extent. **For each symptom, sensation, or type of discomfort listed, we would like you to answer in the following way:**

Please indicate if you have experienced what is described in each sentence, and if the answer is 'yes', how **intense** it was. There are five possible answers, and we would like you to circle the one which best describes your situation.

Circle 1 if you feel the symptom, sensation or discomfort described does not apply to you

•  
•  
•  
•  
•  
C  
i  
r  
c  
i  
e  
2  
,3  
,,

i  
f  
y  
c  
u  
h  
a  
v  
e  
f  
e  
l  
i  
t  
i  
t  
c  
a  
g  
r  
e  
a  
t  
e  
r  
c  
r  
i  
e  
s  
s  
e  
r  
e  
x  
t  
e  
n

•  
•  
•

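### Choosing the phase 3 primary outcome as the least variable QoL score, read as lowest coefficient of variation, depends on how each score is coded

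*Protocol*

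**What the plan says.** The Description gives the pilot's purpose: it is "designed to provide us with enough information for a potentially larger multicentre randomised controlled study". The section on study duration and sample size says how the pilot might help with the choice of outcome: "Hopefully, this will enable us to identify the QoL score with the least variability and use it as the primary outcome measure" of a future phase 3 study.

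The same paragraph names one measure of variability. In an earlier study from the unit, "the coefficient of variation (ratio of standard deviation to mean) was found to increase at the follow-up period and to vary among the different scores", and the authors expect a smaller CV at follow-up in this pilot. The next paragraph uses CV again in its power example, "with a sample size of 208 patients and coefficient of variation of 0.5", with a 15% change in the geometric mean and 85% power. The section gives no minimal important difference, standardised effect or SD of change as a basis for the choice.

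The candidates appear under Secondary Outcome: "Measure and compare the quality of life scores using EQ-5D, AVVQ and CIVIQ at 0 and 3 months". The Objectives tie EQ-5D to the QALY objective: "months (using EuroQoL's EQ-5D) & AVVQ by patients randomised to treatment in the One Stop Vein Clinic". Appendix 8 prints CIVIQ-14 with the instructions "There are five possible answers, and we would like you to circle the one which best describes your situation" and "Circle 1 if you feel the symptom, sensation or discomfort described does not apply to you". Appendix 2 prints the AVVQ items without a scoring rule.

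**The concern.** CV divides the SD by the mean. Adding a constant to a score, or reversing its direction, changes the mean but not the SD, so CV changes although the patients and the information are the same. That is harmless for scores with a true zero and a common direction. The protocol's own material gives reason to doubt this here. CIVIQ-14 items are coded from 1 for no problem, so a simple sum starts at 14 and is high when the patient is worse. EQ-5D is used to compute QALYs, so its value is high when health is good.

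A ranking by CV could therefore favour a score because of its coding. The score chosen might need more phase 3 patients than one passed over. Since informing a larger trial is what the pilot is for, that would weaken one of its intended products.

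**Working it through.** **1. The plan's own example.** Inputs from the sample size section: 208 per group, CV 0.5, 15% in the geometric mean, 85% power. Alpha is not stated there; I assume two-sided 5%.

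- SD on the log scale = √ln(1 + CV²) = √ln(1.25) = 0.472.
- n per group = 2(1.960 + 1.036)² × ln(1 + CV²) / (ln ratio)² = 17.957 × ln(1 + CV²) / (ln ratio)².
- With a ratio of 1.15: 17.957 × 0.2231 / 0.01953 = 205.1, so 206 per group. Power at 208 is 85.5%.

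The example reproduces with 15% taken as a ratio of 1.15. (A literal reduction, ratio 0.85, gives 152.) In this formula CV does drive n once a percentage effect is fixed. The question is whether CV, and that percentage, mean the same thing on each score.

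**2. The same CIVIQ-14 answers under three codings.** From Appendix 8: 14 items, each scored 1 to 5, so a simple sum runs from 14 to 70, a width of 56. The protocol prints no CIVIQ-14 scoring rule and no means or SDs. The three codings and the values below are assumptions for illustration.

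- Raw sum: CV = SD / mean.
- 0–100 index, high worse: mean W = (mean − 14)/56 × 100; SD S = SD/56 × 100; CV = S / W.
- 0–100 index, high better: mean 100 − W, same S; CV = S / (100 − W).

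For mean 24.5 and SD 8: S = 14.29, W = 18.75, 100 − W = 81.25.

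| Assumed raw mean, SD | CV, raw sum | CV, 0–100 high worse | CV, 0–100 high better |
|---|---|---|---|
| 24.5, 8 | 0.33 | 0.76 | 0.18 |
| 20, 6 | 0.30 | 1.00 | 0.12 |
| 35, 12 | 0.34 | 0.57 | 0.34 |

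In each row the CV of 0.5 from the plan's example lies between the lowest and highest entries. A rival score with that CV would rank above or below CIVIQ-14 according to coding alone. The plan does not attribute 0.5 to any instrument, so this shows only how the ranking can turn.

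**3. What happens to the sample size.** Take mean 24.5, SD 8 and an assumed difference of 3 raw points (not a proposed minimal important difference).

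- Raw sum: 3/8 = 0.375 SD.
- Either index: 3/56 × 100 = 5.36 points; 5.36/14.29 = 0.375 SD.
- n per group = 17.957 / 0.375² = 127.7, so 128 in every coding.

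Now apply the step 1 formula with a ratio of 1.15 to the three CVs:

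- Raw sum, CV 0.327: 17.957 × 0.1013 / 0.01953 gives 94 per group.
- High worse, CV 0.762: 17.957 × 0.4577 / 0.01953 gives 421.
- High better, CV 0.176: 17.957 × 0.0304 / 0.01953 gives 28.

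The spread arises because 15% of the mean is a different number of answer steps in each coding. On the 0-based index with high worse there is a further difficulty: a patient who answers 1 throughout scores 0, and the geometric mean is then zero or undefined on the log scale.

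**4. What the documents show for each candidate.** CIVIQ-14: item coding is printed, so the origin and direction of a simple sum follow. EQ-5D: direction follows from its use for QALYs; no zero point is given. AVVQ: neither can be read from the printed items.

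**The case against.** The strongest reply is that the protocol contains no rule to pick the lowest CV. The sentence is a hope about another trial; CV appears nearby as a description of an earlier study and in an example. Any ranking would come after the data are in, the choice would be fixed in the phase 3 protocol, and the details could sit in an analysis plan that is not at hand. Part of this stands: CV as the ranking measure is an inference. It is still the natural one, because the paragraph offers no other measure. Nor is the point about missing detail: the protocol itself states a criterion, and as stated it is unsound for the purpose.

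A second reply is that the plan works with percentage changes in the geometric mean, and for a given percentage effect CV does determine n. That is correct, and step 1 of the working shows it. A reader might infer that CV never tells which score needs fewer patients; that goes too far. It does so when every score has a true zero and the same percentage effect is meaningful on each. The plan's example assumes such an effect and gives no support for applying it across the three scores.

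Third, a reader might infer that all three candidates are shown to differ in both zero and direction. The documents do not show this: they print no scoring rule for AVVQ and no zero for EQ-5D. Fourth, the means, SDs and codings in the working are assumed, and a real trial would use one coding per score. The figures illustrate a general property of CV; they do not show that these scores would be misranked here.

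**Conclusion.** The concern holds in limited form. Read as lowest CV, the stated basis for choosing the phase 3 outcome depends on where each score's zero lies and which end is good. It identifies the score needing the smaller trial only under conditions that the protocol assumes in its example but does not support. That CV depends on origin and direction is a mathematical fact and needs none of the assumed values. The size of the effect does: under the main illustration CV runs from 0.18 to 0.76 for the same answers, while n for a fixed raw difference stays at 128 per group. How far EQ-5D, AVVQ and CIVIQ would be affected in practice cannot be read from the document.

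A reader might also infer that this trial's results are compromised. They are not: no outcome, comparison or sample size in this pilot depends on the sentence. The weight is low, a point to consider.

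**What to change.** In the sample size section, replace smallest variability as the criterion for choosing the phase 3 primary outcome, and state that CVs will be reported descriptively only. For each of EQ-5D, AVVQ and CIVIQ, report the baseline-adjusted SD at 3 months, together with the phase 3 sample size it implies for a minimal important difference on that score's own scale. Source and state those differences in advance, and base the choice on the resulting sample sizes.

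The cost is a change of wording and a short extra analysis; all three scores are already planned at 0 and 3 months. The one new input is a sourced minimal important difference for each score, since the protocol gives none. If a defensible value cannot be found for a score, show its implied sample size over a stated range.
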